#### **6.1.4 Safety Population**

The Safety population will consist of all randomized subjects who have taken at least 1 dose of study treatment. The subjects in this group will be analyzed based on the treatment they received. Subjects who receive treatment from more than 1 arm will be assigned to the voclosporin arm.

### **6.2 Derived Data**

This section describes the derivations required for statistical analysis. Unless otherwise stated, variables derived in the source data will not be re-calculated.

#### **6.2.1 Race**

Where more than one race category has been selected for a subject, these race categories will be combined into a single category labeled “Multiple Race” in the summary tables. The listings will reflect the original selected categories.

#### **6.2.2 Baseline**

Except for parameters detailed later in this section, baseline is defined as the last non-missing value (either scheduled, unscheduled or repeat) before the subject receives the first dose of study drug on Day 1. As assessments on day 1 are scheduled to be undertaken prior to taking study drug, day 1 assessments can be defined as baseline.

eGFR baseline will be calculated as the lowest measurement available prior to dosing.

Urine creatinine baseline will be calculated as the mean of the latest 2 pre-randomization values. Should only 1 value be available it will be used as the baseline value.

Urine protein baseline will be calculated as the mean of the latest 2 pre-randomization values. Should only 1 value be available it will be used as the baseline value.

UPCR values are calculated by the laboratory as the ratio of urine protein to creatinine. The ratio is only calculated where laboratory tests produce a result for both the creatinine and the protein. UPCR baseline will be calculated as the mean of the latest 2 pre-randomization values. Should only 1 value be available it will be used as the baseline value.

For the endpoints of change from baseline in UPCR and also for partial response endpoints (that incorporate a 50% reduction from baseline in UPCR), a second definition of baseline (alternative baseline) UPCR will be defined as the lowest measurement available prior to dosing.

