#### **1.2.4.2 Lupus Nephritis Clinical Development**

The AURA-LV study (Protocol AUR-VCS-2012-01) is a randomized, controlled, double-blind Phase 2 study comparing the efficacy and safety of voclosporin (23.7 mg BID or 39.5 mg BID) with placebo in achieving remission in patients with active LN. The duration of the study is 48 weeks and is ongoing. All patients received background therapy with MMF and corticosteroid taper. The primary endpoint of complete remission was defined as: urine protein creatinine ratio (UPCR) of  $\leq 0.5$  mg/mg at 24 weeks (using first morning void) and eGFR  $\geq 60$  mL/min/1.73 m^2 or no confirmed decrease from baseline in eGFR of  $\geq 20\%$ . In addition, patients could not receive rescue medications for LN (defined as  $>10$  mg prednisone/day for  $>3$  consecutive days or  $>7$  days total from Weeks 16-24) to be considered for complete remission.

A total of 265 subjects were randomized into the AURA-LV study. The 24-week primary endpoint assessment for the AURA-LV clinical study demonstrated that the groups were generally well balanced for age, gender and race, with a trend to higher proteinuria and lower eGFR data in the low-dose voclosporin arm. The low dose achieved a statistically significant benefit over placebo for the primary efficacy assessment of complete remission at 24 weeks (odds ratio (OR) [95% CI] = 2.03, [1.01, 4.05],  $p=0.045$ ), without a statistically significant improvement seen in the high dose. The results were confirmed by 24 hour urine collections ( $p=0.047$ ). Both the low- and high-dose voclosporin were statistically superior to placebo in partial remission, time to complete remission, and time to partial remission. A mean reduction in serum creatinine was seen in both arms (0.2 mg/dL low, 0.1 high;  $p<0.001$ ). In the voclosporin groups, eGFR fell by a median of 8-9 mL/min by Week 4 and then stabilized over the course of the study. Blood pressure did not vary by group. The correlation of 24-hour urine protein and using the first morning void was assessed from the results of the AURA-LV study demonstrating a high degree of correlation (Pearson Correlation Coefficient = 0.92).

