## 4. INVESTIGATIONAL PLAN

### 4.1 Overall Study Design

This is a Phase 3, multicenter, randomized, prospective, double-blind, parallel-group, placebo-controlled, 2-arm comparison study of Orelvo versus matching placebo. Subjects who have provided a signed and dated informed consent will be screened into the study up to 30 days before randomization. During the screening period, eligibility criteria will be assessed. A kidney biopsy may be performed, provided the subject has given consent and provided the results can be obtained and reviewed before baseline. Subjects who meet all of the inclusion criteria and none of the exclusion criteria will be eligible for randomization into the study.

Baseline assessments will be performed before the first dose of study treatment is administered on Day 1. The baseline assessments of the serum creatinine and urine protein laboratory parameters will be established by using the mean of the 2 pre-randomization values. Using an interactive web response system (IWRS), eligible subjects will be randomized to receive either oral Orelvo 23.7 mg BID or matching placebo for 52 weeks. All subjects should receive 0.5 g/day IV methylprednisolone on Days 1 and 2 before changing to a reducing course of oral corticosteroid therapy on Day 3. (For additional details and exceptions, see Section 7.2.2.2, [Corticosteroids](#)). Starting at the Baseline Visit, all subjects will also receive background therapy with MMF (see Section 7.2.2.3, [Mycophenolate Mofetil \(Background Therapy\)](#)).

All subjects will return for assessment of efficacy and safety at Day 2 and Weeks 2, 4, 8, 12, 16, 20, 24, 30, 36, 42, 48, and 52. See [Schedule of Events](#), for detailed information regarding visits. In addition, subjects not on MMF during screening, will start receiving MMF at the Baseline Visit and will return for local complete blood count assessments at Weeks 1 and 3 after randomization.

All subjects, completed or withdrawn, will complete the End of Treatment/Early Termination assessments (Visit 15) at Week 52 or at the time of early termination. Subjects who do not enroll in the continuation study will attend the Safety Follow-up Visit (Visit 16) at Week 56 to collect any new AEs and concomitant medications. At the follow-up visit, UPCR and eGFR will be assessed as well. For subject withdrawal procedures and criteria, see Section 5.5, [Withdrawal of Subjects](#).

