### **7.6.1 Deterioration in Renal Function**

Serum creatinine and eGFR utilizing the CKD-EPI formula will be used for the assessment of renal function at every visit (Visits 1-15 and unscheduled visit(s)). Subjects will have a minimum of 2 eGFR measurements conducted prior to dosing at Visit 2. The lowest of the pre-dose eGFR assessments will be used as the marker of baseline renal function.

It is recognized that eGFR may be unreliable at higher values ( $>100$  mL/min/1.73 m^2). Lupus nephritis subjects with nephrotic range proteinuria frequently have wide fluctuations in serum creatinine (and therefore eGFR) which are not representative of true renal dysfunction. Chronic kidney disease is defined as eGFR  $<60$  mL/min/1.73 m^2 for  $\geq 3$  months [20], with or without kidney damage.

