Notes: FMV = first morning void; HDL = High-density lipoprotein; LDL = Low-density lipoprotein; UPCR = urine protein creatinine ratio.  
Baseline renal function will be the minimum value of any and all eGFR values taken during the screening period and at baseline prior to administration of drug (a minimum of the screen and baseline (pre-dose) values. The central lab will need to report a baseline value for the analysis.

The total amount of blood that will be collected during the study from an individual subject is approximately 300 mL over 56 weeks.

For details on whether laboratory abnormalities should be reported as AEs and on the follow-up required in such cases, see Section 10.2.5, [Clinical Laboratory Evaluations](#).

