#### **6.11.4.6 Change from baseline in eGFR**

Estimated glomerular filtration rate (eGFR) will be measured at all visits except Visit 2. The response variable change from baseline in eGFR will be summarized at Weeks 2, 4, 8, 12, 16, 20, 24, 30, 36, 42, 48 and 52 (Table 14.2.11.1). Baseline is calculated as defined in Section 6.2.2.

These change from baseline tables will be produced using both corrected and raw eGFR values.

Listings of this endpoint will be provided with lab data.

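### Measuring eGFR from the lowest pre-dose value makes each arm's eGFR loss and confirmed >30% decreases look smaller; add a supplementary mean-baseline analysis

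*SAP*

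**What the plan says.** SAP 6.2.2 states that "eGFR baseline will be calculated as the lowest measurement available prior to dosing". This is also the protocol's rule. Protocol 7.6.1 says "The lowest of the pre-dose eGFR assessments will be used as the marker of baseline renal function", the note under Table 2 says "Baseline renal function will be the minimum value of any and all eGFR values taken during the screening period and at baseline", and 9.2.1 repeats it. Protocol 7.6.1 adds: "Subjects will have a minimum of 2 eGFR measurements conducted prior to dosing at Visit 2".

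The baseline feeds two eGFR endpoints:

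- **SAP 6.11.4.6, change from baseline in eGFR**, at twelve visits from Week 2 to Week 52: "Baseline is calculated as defined in Section 6.2.2". Under SAP 6.11.4 the mixed model gives between-arm differences, and also least-squares means for each arm by visit, with plots for eGFR.
- **SAP 6.11.4.2, confirmed >30% decrease.** The fall must be seen at two consecutive time points. Proportions are shown by arm and visit, with p-values from a chi-square or Fisher test. No other baseline is named.

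For UPCR, SAP 6.2.2 takes the mean of the latest two pre-randomization values and adds the lowest pre-dose value as an alternative baseline for supplementary analyses. I found no such alternative for eGFR. SAP 6.2.13 (eGFR) is in the contents list, but its text was not in the copy I read, so a further rule there cannot be excluded.

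**The concern.** The baseline is a minimum of at least two values. Each follow-up value is a single one, because SAP 6.2.11 tabulates the latest observation per visit. Comparing an ordinary later value with a selected low one moves the change upwards even when kidney function has not altered. The shift grows with the number of pre-dose tests and with their scatter. Protocol 7.6.1 itself says that eGFR in these subjects often fluctuates widely without true dysfunction.

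The drug is a calcineurin inhibitor. Protocol 1.2.4.2 reports that in Phase 2 "eGFR fell by a median of 8-9 mL/min by Week 4" in the voclosporin groups. If the baseline shift is of similar size to the effect being looked for, the per-arm eGFR tables and plots, and the counts of confirmed >30% decreases, will look more reassuring than they should.

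**Working it through.** The documents state no figure for the size of this effect, so there is none to reproduce. The direction follows from algebra. The size needs assumptions.

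**Step 1. Direction, for every subject.** Let m be the lowest and a the mean of the same pre-dose values, and y a follow-up value. Since m ≤ a, y − m ≥ y − a and y/m ≥ y/a. A fall measured from the lowest value is therefore never larger than one measured from the mean. Anyone counted as a >30% decrease from m is also counted from a, but not the reverse. Example: with pre-dose values of 100 and 80, the cut-off is 0.7 × 80 = 56. The mean is 90, and 1 − 56/90 = 37.8%. The 30% rule acts as a 37.8% rule against the mean.

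**Step 2. Size of the baseline shift.** For two independent normal values with mean μ and within-subject SD σ, the expected minimum is μ − σ/√π = μ − 0.564σ. Assume μ = 90 and σ = CV × 90:

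| Assumed CV | σ | Shift 0.564σ (mL/min) |
|---|---|---|
| 5% | 4.5 | 2.5 |
| 10% | 9.0 | 5.1 |
| 15% | 13.5 | 7.6 |
| 20% | 18.0 | 10.2 |

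**Step 3. Effect on the endpoints, by simulation.** About half a million subjects per arm. All inputs are assumed:

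- True baseline normal with mean 90 and SD 30, kept between 45 and 150.
- Two pre-dose values and two follow-up values, each with multiplicative error at the stated CV.
- True mean loss 9.4% on drug (8.5/90, the middle of the Phase 2 range over 90) and 0% on placebo, with SD 15% between subjects.
- Confirmed decrease means that both follow-up values are below 0.7 × baseline.

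Mean change from baseline (mL/min):

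| CV | Drug, lowest | Drug, mean | Placebo, lowest | Placebo, mean | Difference, lowest | Difference, mean |
|---|---|---|---|---|---|---|
| 5% | −6.11 | −8.72 | +2.63 | +0.01 | −8.74 | −8.72 |
| 10% | −3.51 | −8.75 | +5.31 | +0.07 | −8.81 | −8.82 |
| 15% | −0.89 | −8.79 | +7.98 | +0.08 | −8.87 | −8.88 |
| 20% | +1.81 | −8.83 | +10.67 | +0.06 | −8.87 | −8.90 |

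Confirmed >30% decrease (drug v placebo; RD = risk difference in points, RR = risk ratio, from unrounded values):

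| CV | Lowest baseline | RD | RR | Mean baseline | RD | RR | RD lost |
|---|---|---|---|---|---|---|---|
| 5% | 5.85% v 1.49% | 4.36 | 3.92 | 7.40% v 2.00% | 5.40 | 3.71 | 1 − 4.36/5.40 = 19% |
| 10% | 4.96% v 1.38% | 3.57 | 3.58 | 7.63% v 2.33% | 5.30 | 3.27 | 1 − 3.57/5.30 = 33% |
| 15% | 4.90% v 1.64% | 3.25 | 2.98 | 8.81% v 3.31% | 5.50 | 2.66 | 1 − 3.25/5.50 = 41% |
| 20% | 5.35% v 2.19% | 3.16 | 2.44 | 10.56% v 4.86% | 5.70 | 2.17 | 1 − 3.16/5.70 = 45% |

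With three pre-dose values and CV 10%, the risk difference is 2.73 against 5.12 points, a loss of 47%.

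**Step 4. Neighbouring baseline rules.** Protocol 4.1 says that serum creatinine and urine protein baselines "will be established by using the mean of the 2 pre-randomization values". SAP 6.2.2 lists exceptions for eGFR, urine creatinine, urine protein and UPCR, but none for serum creatinine, so its default of the last non-missing pre-dose value applies. The two documents differ on creatinine. Separately, SAP 6.11.4.6 says that eGFR is not measured at Visit 2, which is Day 1. Protocol Table 2 excludes Day 2, which the Schedule of Events labels Visit 3. Read literally, the SAP sentence would remove the second scheduled pre-dose value that protocol 7.6.1 requires.

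**The case against.** - **The rule is deliberate.** It stands in three places in the protocol, and the Table 2 note ties it to the value used for analysis. A reader might infer that the SAP departs from the protocol, or that protocol 4.1 contradicts the eGFR rule. Neither is supported: the documents agree on eGFR, and 4.1 covers serum creatinine and urine protein only. This stands, and it argues against replacing the baseline.
- **The randomized comparison of means is sound.** A reader might infer that the treatment effect on mean eGFR is understated. It is not: randomization gives both arms the same expected shift, so the difference is unchanged at every CV tried. The risk ratio is not reduced either. This stands. The per-arm means, plots and proportions remain affected.
- **Pre-dose eGFR may not be stable.** Subjects enter with active disease. If eGFR falls through screening, the lowest value is also the latest, and a mean baseline would count pre-treatment decline as on-treatment loss. This stands as a condition on the conclusion.
- **The Phase 2 fall cannot be re-scaled.** It is tempting to say that the 8-9 mL/min seen there would shrink to about half here. The protocol does not say how Phase 2 baseline eGFR was defined, so that figure may already contain the shift.
- **Other renal data exist.** Serum creatinine change is reported at the same visits, from a baseline that is not a minimum. That is a partial cross-check, but it gives no >30% eGFR proportion. The >30% endpoint is outside the key secondary testing procedure (SAP 9), yet its p-values are still reported.
- **Replacing the baseline would create a mismatch** with the >20% criterion in the response definition. With pre-dose values of 100 and 60 and two follow-ups of 55, the fall is 25/80 = 31% from the mean but 5/60 = 8% from the lowest. The subject would have a confirmed >30% decrease without a >20% one. This stands, and favours a supplementary analysis.

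**Conclusion.** The concern holds in a limited form. Falls from the lowest pre-dose value are never larger than falls from the mean; that needs no assumption. If pre-dose eGFR is stable, per-arm eGFR change, per-arm proportions with a confirmed >30% decrease, and the risk difference between those proportions understate loss.

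The size rests wholly on assumed variability, because the documents give none. For CV 5% to 20%, true levels around 90 and two pre-dose values, the baseline shift is about 2.5 to 10 mL/min, and the risk difference is cut by roughly 20% to 45%. No single point in that range can be preferred from the documents. Nor can one say as a fact that the placebo arm will appear to gain eGFR; that is a result of the assumed model.

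This is an inexpensive improvement to the renal safety outputs. It does not show that the pre-specified rule is invalid.

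**What to change.** 1. Keep the lowest pre-dose value as the main eGFR baseline. Add to SAP 6.2.2 an alternative eGFR baseline equal to the mean of the pre-dose values (screening and Day 1), using the single value where only one exists, as for UPCR.
2. Add supplementary analyses of SAP 6.11.4.2 and 6.11.4.6 on that baseline, mirroring the alternative-baseline analyses for UPCR.
3. Reconcile the serum creatinine baseline: mean of two values in protocol 4.1, last value by default in SAP 6.2.2.
4. Reconcile the Visit 2 statement in SAP 6.11.4.6 with protocol Table 2 and 7.6.1, since the alternative baseline depends on the Day 1 value.

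The cost is some SAP wording and a few repeated tables, with no new data. Reported eGFR declines will look somewhat worse in the supplementary tables. The primary endpoint definition and the protocol's care rules are not touched.

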### **3.2.2 Other Secondary Endpoints**

- Duration of UPCR  $\leq 0.5$  mg/mg
- Change from baseline in UPCR at each time point
- Change from baseline in serum creatinine, urine protein, and eGFR at each time point

- Proportion of subjects experiencing a confirmed >30% decrease from baseline in eGFR at each time point
- Change from baseline in immunology parameters (complement 3 (C3), C4, and anti-double-stranded deoxyribonucleic acid (dsDNA)) at Weeks 24 and 52
- Renal response with low-dose steroids at Weeks 24 and 52 (defined as renal response in the presence of corticosteroids of  $\leq 2.5$  mg/day between Weeks 16 to 24 and Weeks 44 to 52)
- Change from baseline in health-related quality of life (HRQoL) at Weeks 12, 24, and 52
- Health Resource Utilization at Weeks 24 and 52
- Change from baseline in the Safety of Estrogens in Lupus Erythematosus National Assessment - Systemic Lupus Erythematosus Disease Activity (SELENA-SLEDAI) Index score at Weeks 24 and 52

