#### **6.11.4.4 Change from baseline in serum creatinine**

Serum creatinine data will be available in lab data. The response variable, change from baseline in serum creatinine, will be summarized at Weeks 2, 4, 8, 12, 16, 20, 24, 30, 36, 42, 48 and 52 (Table 14.2.9). Listings of this endpoint will be provided with lab data. Baseline is calculated as defined in Section 6.2.2

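### The protocol sets a mean-of-two baseline for serum creatinine; the SAP leaves it on the last single pre-dose value and does not declare the change

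*SAP*

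**What the plan says.** Protocol 4.1 is explicit: "The baseline assessments of the serum creatinine and urine protein laboratory parameters will be established by using the mean of the 2 pre-randomization values".

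SAP 6.2.2 opens with a general default: "baseline is defined as the last non-missing value (either scheduled, unscheduled or repeat) before the subject receives the first dose". It then lists exceptions. eGFR takes the lowest pre-dose value. Three urine measures take a mean of two: "Urine creatinine baseline will be calculated as the mean of the latest 2 pre-randomization values"; "Urine protein baseline will be calculated as the mean of the latest 2 pre-randomization values"; and UPCR has the same rule. Each of the three falls back to one value if only one exists. Serum creatinine is not among the exceptions.

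SAP 3.2.2 lists the endpoint among the other secondary endpoints: "Change from baseline in serum creatinine, urine protein, and eGFR at each time point". SAP 6.11.4.4 says of it "The response variable, change from baseline in serum creatinine, will be summarized at Weeks 2, 4, 8, 12, 16, 20, 24, 30" and continues to Week 52. For the baseline it says only "Baseline is calculated as defined in Section 6.2.2".

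SAP Section 1 restates much of the protocol 4.1 design text but omits the sentence on the mean of two values. SAP Section 9, on changes from the protocol analysis, covers the region term and the key secondary list, and nothing on baselines.

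**The concern.** The two documents give two baselines for one named endpoint. A programmer who follows the SAP will not produce the analysis in the protocol, and nothing in the SAP tells a reader that a choice was made. An undeclared difference of this kind is best settled before unblinding, because afterwards either choice can look driven by results.

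Precision may also be lost. Protocol 7.6.1 itself warns that serum creatinine fluctuates widely in subjects with nephrotic-range proteinuria, which is the setting where averaging two readings usually helps. The parameter matters for a calcineurin inhibitor, and the same baseline would feed the serum chemistry change tables in SAP 6.13.2.

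**Working it through.** **The plan's own figure.** The documents state no SD, correlation or power for serum creatinine. The only design figure is 162 per arm for the primary endpoint (SAP Section 4: 20.0% against 34.4%, two-sided 0.05, 80% power, continuity-corrected chi-square). Recomputing gives 163 per arm with the correction and 149 without it, so the stated figure reproduces to within one subject. I use 162 per arm below.

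**Which baseline applies.**
1. Protocol 4.1: serum creatinine and urine protein, mean of two.
2. SAP 6.2.2: urine creatinine, urine protein and UPCR, mean of two; eGFR, lowest; everything else, last value.
3. SAP 6.11.4.4 points to 6.2.2 and adds no rule of its own.
4. So urine protein agrees with the protocol and serum creatinine does not.

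The urine creatinine rule does not meet the protocol requirement by another route. It concerns a different specimen, and UPCR does not depend on it: "UPCR values are calculated by the laboratory as the ratio of urine protein to creatinine", with its own baseline rule.

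**Are two values available?** Protocol Table 2 and the Schedule of Events place blood chemistry at screening and Day 1, and protocol 7.6.1 requires at least two eGFR values before dosing. Two pre-dose values are therefore planned.

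**Size of the precision effect (assumed inputs).** Take equal variances and one common correlation r among screening, Day 1 and follow-up. In SD² units, the residual variance with baseline as covariate is

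- single baseline: 1 − r²
- mean of two: 1 − 2r²/(1 + r)

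The 95% half-width for a treatment difference at one visit is 1.96·√(2v/162), where v is that residual variance.

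| r | v, single | v, mean of two | reduction | SE ratio | half-width (SD) |
|---|---|---|---|---|---|
| 0.5 | 0.750 | 0.667 | 11% | 0.943 | 0.189 to 0.178 |
| 0.7 | 0.510 | 0.424 | 17% | 0.911 | 0.156 to 0.142 |
| 0.8 | 0.360 | 0.289 | 20% | 0.896 | 0.131 to 0.117 |
| 0.9 | 0.190 | 0.147 | 22% | 0.881 | 0.095 to 0.084 |

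For an unadjusted change score the variances are 2(1 − r) and 1.5(1 − r), a 25% reduction at any r. The SAP model code under 6.11.4 carries a baseline term, so the table is the relevant comparison if that term is the endpoint's own baseline.

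Simulation with 162 per arm and 2,000 runs gave SE ratios of 0.938, 0.914 and 0.880 at r = 0.5, 0.7 and 0.9. With a true difference of zero, the mean estimates under both baselines lay within 0.002 SD of zero.

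**When the two readings are not equally informative.** Let the two baselines correlate 0.8, Day 1 and follow-up 0.7, and screening and follow-up s. The single Day 1 baseline leaves 1 − 0.49 = 0.51. The mean of two leaves 1 − (0.7 + s)²/3.6.

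- Break-even: (0.7 + s)² = 0.49 × 3.6 = 1.764, so s is about 0.63.
- s = 0.60: 1 − 1.69/3.6 = 0.531, which is 4% higher than 0.51.
- s = 0.55: 1 − 1.5625/3.6 = 0.566, which is 11% higher.

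**The case against.** The strongest reply is that little turns on this. The endpoint is an other-secondary one, outside the Hochberg family, and is listed under efficacy. Renal function in the primary endpoint and in the dose-modification rules runs on eGFR, whose baseline (lowest pre-dose value) is the same in both documents. That stands, and it limits the reach of the point.

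The precision argument can also be challenged. No document supplies a correlation, and a screening value up to 30 days old may track follow-up less well than Day 1. That stands too: the gain depends on assumptions and can reverse. The case for a correction rests on the conflict between the texts, not on the percentage.

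A third objection concerns wording. Copying the protocol's pre-randomization phrase into the SAP could misfire. Day 1 is also the randomization day, and the documents require procedures before first dose, not before randomization. Blood drawn on Day 1 after randomization would be excluded, and a one-value fallback would then use only the older screening value. This is correct, and the fix below is worded accordingly.

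A reader might infer that urine was simply written for serum and that the urine creatinine sentence should go. The documents do not show that. The version 5.0 amendment entry names the urine creatinine baseline, which suggests a deliberate edit, and SAP 6.13.2 summarises change from baseline for continuous urinalysis parameters, so urine creatinine needs a baseline.

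**Conclusion.** The conflict is real and needs no calculation: protocol 4.1 requires a mean of two for serum creatinine, the SAP applies the last single value, and Section 9 is silent. It should be corrected, but it affects only the serum creatinine change endpoint and the serum chemistry change summaries.

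A reader might go further and infer bias, or a threat to the trial's renal conclusions. Neither follows. Both baselines are unbiased for the treatment difference under randomization, and the primary endpoint, eGFR, UPCR, key secondary endpoints and sample size do not use this baseline. Nor can a definite loss of precision be claimed. The reduction of about 11% to 22% assumes a common correlation of 0.5 to 0.9, equally informative screening and Day 1 values, and the endpoint's own baseline as the covariate.

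**What to change.** In SAP 6.2.2, add that serum creatinine baseline is the mean of the latest two values before first dose (normally screening and Day 1), with the single value used if only one is available. Referring to first dose keeps the Day 1 reading eligible whatever its order relative to randomization.

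If the last single value is what the sponsor wants, say so in SAP Section 9 as a departure from protocol 4.1 and give the reason.

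In either case, confirm that the urine creatinine rule is intended and, if so, keep it.

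The cost is a sentence or two and one derivation in the analysis programs. No new data, visits or subjects are needed.
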